### 3.0 Objectives

**Aim 1: Elucidate merits of transdiagnostic sampling.** Within the two intervention groups (Group 1: n = 24, Active iTBS and Active iTBS + APT; Group 2: n = 24, Placebo iTBS and Placebo iTBS + APT), we expect that (1i) neurologic diagnosis (stroke, TBI) will not moderate the effect of Active iTBS or Active iTBS + APT on Maximum Cognitive Gain as assessed by the Modified Digit Span (MDS) and the Streamlined AMPS (AMPS).

**Aim 2: Obtain pilot data to inform estimation of treatment and practice effects.** We will gather pilot data regarding the magnitude and duration of treatment effects as well as MDS and AMPS practice effects. As we anticipate (2i) greater immediate gains in IADL performance (AMPS) after Active iTBS + APT when compared to Active iTBS alone, we will compare Maximum Cognitive Gains (MCG) on MDS with MCG on AMPS between the Active iTBS and Active iTBS + APT groups to determine if MCGs differ in magnitude. We will also determine if

Active iTBS + APT trend lines indicate an additive treatment effect of APT on MDS and/or AMPS. We also anticipate (2ii) some persisting treatment effects and to explicate these effects we will examine effects for Active iTBS and Active iTBS + APT in the short-term (post-pre-treatment), long-term (2 weeks after a session) and cumulatively across treatment sessions. Since the AMPS uses a unique task during each testing interval and MDS uses 1 of 6 alternate test forms, we will determine (2iii) presence and magnitude of practice effects by testing whether prior exposure to MDS or AMPS results in MDS or AMPS gains for Placebo iTBS.

**Aim 3: Explicate study attrition by perceived suitability of aspects the study design and the relationship between this perceived suitability and fatigue as well as mood.** We will test the ideas that (3i) Attrition rates do not differ by stroke and TBI groups, (3ii) Veterans across stroke and TBI have similar perceptions regarding suitability of the number and type of tests as well as number of study-days, and (3iii) perceived suitability is related to Veteran-reported fatigue and mood.

Aligned with VA RR&D's mission to create knowledge and innovations advancing the rehabilitative health and care of Veterans, this project will scale-up the scientific basis for developing and, ultimately, delivering Veteran-tailored, interventions that improve the aspects of function identified by Veterans across neurologic diagnoses as important to their well-being. For Veterans with moderately impaired levels of cognition who are struggling with daily life, thereby requiring assistance with complex instrumental activities of daily living, this project will explicate critical and practical barriers to developing Veteran-tailored interventions that optimize cognitive function in daily life. The results will be used to design and conduct future merit research examining the over-arching hypothesis that restorative cognitive interventions developed according to transdiagnostic sampling and matched with a biotype algorithm, compared to a diagnosis-based algorithm, result in better functional performance of Veteran-valued IADL.

With additional supplemental funds awarded through the Infinite Hero Foundation administered through Northwestern University Feinberg School of Medicine Department of Physical Medicine and Rehabilitation, two additional aims have been added to this study. With the provide funds, the study will enable all Veteran participants enrolled in the Pilot study to have their baseline fMRI to be collected at Northwestern University Clinical Translational Imaging (NU CTI) center located at Olson Pavilion at [name].

Secondly, it will provide additional optional treatment for up to 12 enrolled Veterans with a diagnosis of Traumatic Brain Injury who have enrolled and completed the main study. Participants with the diagnosis of Stroke will not be eligible to participate in the Optional Experimental Treatment sessions.

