For measuring immediate changes in cognitive function, we will use the aforementioned **AMPS**. For each of the *three administrations, in 30-min intervals*, a unique task will be randomly selected (without replacement) from the set of tasks developed during Step 4 (Fig 1). Thus, the same IADL is never repeated for the same Veteran.

**Persisting Effects (PE) Measures.** This battery includes the same five tests/sub-tests administered during screening (Fig 1, Step-4: AMPS, RBANS, WAIS-IV Digit Span, DKEFS subtests and BRIEF-A). As the BRIEF-A will be re-administered, the study Neuropsychologist will review BRIEF-A scores and, if there are compelling reasons, Veterans with scores suggesting atypical validity will be withdrawn. This battery also includes tests to measure change in mood: Columbia Suicide Severity Rating Scale (C-SSRS) *Beck Anxiety Inventory (BAI)*, and the *Posttraumatic Stress Disorder Checklist (PCL)*. To assess fatigue, we will use the Fatigue Severity Scale (FSS), which is a self-report measure of prior-week fatigue during nine activities and current fatigue. To measure behavioral features of agitation, we will use the *Agitated Behavioral Scale (ABS)*.

Table 2: Instrumentation: Testing Battery					
Immediate Outcome Effects (ImE)	Hrs/Admin	Aims	Variable Types	# Reps	
AMPS	1.5	1 & 2	Continuous (logit)	3	
Modified Digit Span (MDS)	0.2	1 & 2	Proportional (% correct)	3	
Persisting Effects Testing Battery (PE)	Hrs/Admin	Aims	Variable Types	# Reps	
Repeatable Battery for Assessment of Neuropsych Status (RBANS)	1.0	2	Continuous (normed score)	5	
Weschler Adult Intelligence Scale (WAIS-IV) Digit Span			Proportional (% correct)	5	
Delis-Kaplan Executive Functioning System (DKEFS): Color-Word			Continuous (normed score)	5	
Behavior Rating Inventory of Executive Function (BRIEF)			Continuous (normed score)	5	
AMPS	1.5	2	Continuous (logit)	5	
PTSD Checklist (PCL)	0.1	2 & 3	Mean # symptoms/ severity	5	
Columbia Suicide Severity Rating Scale (C-SSRS)	0.1	2 & 3	Raw score (Veteran rating)	5	
Beck Anxiety Inventory (BAI)	0.1	2 & 3	Raw score (Veteran rating)	5	
Agitated Behavior Scale (ABS)	0.1	2 & 3	Raw score (research clinician rating)	5	
Fatigue Severity Scale (FSS): Prior Week Daily Living Score	0.1	2 & 3	Raw score (Veteran rating)	5	
Fatigue Severity Scale (FSS) L VASF Current Fatigue Rating	0.1	2 & 3	Raw score (Veteran rating)	5	

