## 5.6 Data Analysis

**Sample Size to Estimate Effect Sizes.** Our total sample size of 48 participants is based on 80% power to detect an Effect Size (ES) of .90. For 80% power, sample size per group to detect a small ES (0.35) is 130, for a medium ES (0.60) it is 42 and to detect a large ES (0.90) it is 21 per group. To estimate a large ES of 0.90, 42 subjects are required to achieve 80% power. Thus, we plan for 48 participants and 12% attrition.

Published methods  will be used to examine the merits of transdiagnostic sampling (Aim 1i). Specifically, we will use MLM to determine if neurologic diagnosis (stroke, TBI) moderates the effects of the Active intervention (Group 1: n = 24, Active iTBS and Active iTBS + APT; Group 2: n = 24, Placebo iTBS and Placebo iTBS + APT) on Maximum Cognitive Gain (MCG) as measured with the MDS and the AMPS.

For Aim 2, we will inform estimates of effect sizes by testing the idea (2i) that MDS gains and AMPS gains differ for Active iTBS and Active iTBS + APT. As specified in Table 1, we will examine if gains differ in magnitude by computing the MCGs for each outcome (MDS and AMPS) by each intervention. For each outcome, we will compare the Average Active iTBS MCG with the Average Placebo iTBS MCG and the Average Active iTBS + APT MCG with the

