Average Placebo iTBS + APT MCG using t-tests for continuous data and z-tests for binary data. Using MLM, we will also determine if Active iTBS is related to more MDS or more AMPS gains. The group (Active iTBS or Placebo iTBS) by time interaction parameter will be used to examine if Active iTBS has a differential trend compared to Placebo iTBS. For 2i, we will also use MLM to identify presence of an additive effect of APT by examining Active iTBS + APT trend lines. For both the AMPS and the MDS outcomes, the group (Active iTBS + APT or Placebo iTBS + APT) by time interaction parameter will be used to examine if the Active iTBS + APT has a differential trend compared to Placebo iTBS + APT. For each intervention we will also determine (2ii) presence of persisting effects of Active iTBS and Active iTBS + APT in the short-term, long-term and cumulatively. Using the PE measures specified in Table 1 and t-tests, we will compare each PE measure for Active iTBS with Placebo iTBS and for Active iTBS + APT with Placebo iTBS + APT. Significant results will be reported. For (2iii), we will use one-tailed t-tests to identify presence of practice effects for MDS and AMPS. We will compare MDS and AMPS average peak gains after Placebo iTBS with average peak gains after Active iTBS. If the average Placebo iTBS peak gain is greater than the average Active iTBS peak gain for either MDS or AMPS, then we will repeat analyses above (for 2i and 2ii) using ImE and PE measures after adjusting them for the detected practice effects.

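### Aim 2i asks whether gains are larger on MDS or on AMPS, but one is in per cent correct and the other in logits, with no common scale stated

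*Combined protocol and SAP*

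**What the plan says.** The cross-outcome question appears in three places.

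- Section 3.0, Aim 2: "we will compare Maximum Cognitive Gains (MCG) on MDS with MCG on AMPS between the Active iTBS and Active iTBS + APT groups".
- Section 5.6, restating 2i as the idea "that MDS gains and AMPS gains differ for Active iTBS and Active iTBS + APT".
- Section 5.6, on the mixed model: "Using MLM, we will also determine if Active iTBS is related to more MDS or more AMPS gains".

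Table 2 in section 5.5 gives the variable type of MDS as "Proportional (% correct" and of AMPS as "Continuous (logit" (closing brackets omitted). The text of section 5.5 confirms that AMPS raw scores are converted to logits.

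The tests that section 5.6 actually sets out are of another kind. The t-tests are by outcome: "For each outcome, we will compare the Average Active iTBS MCG with the Average Placebo iTBS MCG", and likewise for iTBS + APT. The only mixed-model parameter named is the group "by time interaction parameter will be used to examine if Active iTBS has a differential trend compared to Placebo iTBS"; for iTBS + APT it is to be examined for AMPS and for MDS.

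Section 5.6 refers to Table 1 for how the maximum cognitive gain (MCG) is computed. Table 1 in this document is the list of eligibility criteria, so the reference leads to no definition of MCG or its scale.

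**The concern.** Asking which of two outcomes gained more needs a scale on which both can be read. A percentage-point gain and a logit gain have none, and nothing in the plan supplies one (z-score, standardised gain or other). Table 2 does not settle whether MDS will be analysed as 0–100 or 0–1, and that choice alone can reverse the ranking.

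The within-outcome analyses do not fill the gap. Two group-by-time slopes, one per outcome, are still in different units. Comparing two p-values is not a test of a difference.

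Aim 2 exists to inform effect-size estimates for a later crossover trial. A statement that iTBS moves working memory more than daily function, or the reverse, could be carried into that design although it rested on a coding choice.

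The design adds a second limit. Under section 5.1 each Veteran takes one immediate-effects test on Study-Day 2 and the other on Study-Day 3. Within a session, an MDS-versus-AMPS contrast is between different Veterans. Within a Veteran, it is mixed up with iTBS alone versus iTBS + APT.

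**Working it through.** **The plan's own figure.** Section 5.6 states 21 per group for an effect size of 0.90 at 80% power. Assuming two-sided alpha 0.05 (not stated), the normal formula gives 2 × (1.960 + 0.842)² / 0.90² = 19.4, so 20; the t-based solution is 20.4, so 21. Then 42 / (1 − 0.12) = 47.7, so 48. This reproduces. It uses a standardised effect and does not rest on the cross-outcome comparison.

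**When the raw ranking reverses.** Let the MDS gain be m percentage points and the AMPS gain a logits, both positive. Coded 0–100, MDS ranks first if m > a. Coded 0–1, it ranks first if m/100 > a. The ranking reverses whenever m/100 < a < m.

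**Worked case.** The documents give no gains or SDs, so these are assumed: MDS +9 points (SD 10), AMPS +0.45 logit (SD 0.5). Section 5.1 splits each group of 24 between the two tests, so n = 12 per test.

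- Standardised: 9/10 = 0.90 and 0.45/0.5 = 0.90, hence equal.
- Raw, MDS 0–100: (9 − 0.45) / √(100/12 + 0.25/12) = 8.55 / 2.89 = 2.96, in favour of MDS.
- Raw, MDS 0–1: (0.09 − 0.45) / √(0.01/12 + 0.25/12) = −0.36 / 0.147 = −2.45, in favour of AMPS.

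**Range.** Simulation with 20,000 runs per row, n = 12 per outcome, and a Welch t-test of raw MDS gain against raw AMPS gain. The AMPS SD is 0.5 throughout. Percentages are runs with p < 0.05 in the stated direction.

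| MDS gain (SD), points | AMPS gain, logits | Standardised MDS / AMPS | Coded 0–100: MDS more / AMPS more | Coded 0–1: MDS more / AMPS more |
|---|---|---|---|---|
| 9 (10) | 0.45 | 0.90 / 0.90 | 78% / 0% | 0% / 61% |
| 10 (15) | 0.30 | 0.67 / 0.60 | 53% / 0% | 0.1% / 24% |
| 5 (15) | 0.50 | 0.33 / 1.00 | 16% / 0.2% | 0% / 79% |
| 15 (15) | 0.20 | 1.00 / 0.40 | 87% / 0% | 1.2% / 5.1% |
| 4.5 (15) | 0.45 | 0.30 / 0.90 | 13% / 0.2% | 0% / 70% |
| 13.5 (15) | 0.15 | 0.90 / 0.30 | 80% / 0% | 2.0% / 3.3% |

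In all six rows the larger raw mean is MDS under one coding and AMPS under the other, whichever outcome has the larger standardised gain.

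**Within-outcome check.** An Active-versus-Placebo t-test on one simulated set of MDS gains gave t = 0.642, p = 0.527 under both codings. The planned within-outcome tests do not depend on units.

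**The case against.** The strongest reply is that the plan never writes down the offending test. Its t-tests are by outcome, its named mixed-model parameter is group by time, and no group-by-outcome term or subtraction of an AMPS gain from an MDS gain appears. The sentence about more MDS or more AMPS gains can be read as one model per outcome. The effect anticipated under 2i, greater AMPS gain after iTBS + APT than after iTBS alone, is in logits on both sides. The test given first is randomly assigned, so having different Veterans within a session is not in itself a bias. And Aim 2 is pilot work.

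All of this stands, and it limits the point. A reader might infer that the treatment tests are compromised, or that the answer to which outcome gains more depends only on units and not on treatment. The documents support neither. The specified tests are unit-free. The size and significance of a raw difference also depend on the true gains and SDs, as the table shows. Some rankings do not reverse at all: with a 15-point MDS gain, any AMPS gain below 15/100 = 0.15 logit ranks MDS first under either coding.

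What the reply does not remove is the question itself, posed in the aim, in the restated hypothesis and in the analysis text. The within-outcome tests cannot answer it.

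**Conclusion.** The point holds in a limited form. The cross-outcome part of Aim 2i has no stated common scale, and a ranking of raw gains or slopes can reverse with the coding of MDS. In the equal-effect example, it goes from 78% of runs favouring MDS to 61% favouring AMPS. These percentages rest on assumed gains and SDs, normal gains and 12 Veterans per test; the condition m/100 < a < m does not. The within-outcome Active-versus-Placebo tests, the group-by-time terms, the AMPS-to-AMPS contrast anticipated under 2i and the sample size are not affected by this problem.

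**What to change.** 1. Define MCG in section 5.6 and correct the reference to Table 1. State the score from which the gain is measured: the Study-Day 2 and 3 lists show MDS only after the intervention.
2. For each outcome and session, report the Active-minus-Placebo difference in MCG divided by that outcome's own SD of MCG, with a 95% CI. Choose the pooled or the placebo-group SD in advance.
3. Base any MDS-versus-AMPS statement only on the difference between these standardised effects, with its CI, and note that within a session the two outcomes come from different Veterans.
4. Otherwise, delete the cross-outcome comparison and confine 2i to within-outcome contrasts.

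Baseline SDs are a less suitable divisor. The AMPS baseline is truncated by the entry rule of below 1.0 logits, and WAIS-IV Digit Span would be a different instrument standing in for MDS.

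The cost is analysis wording only; no data collection changes. The downside is precision, because the SDs come from about 12 Veterans per arm per test and session. For a standardised effect of 0.90 with 12 per arm, the approximate SE is √(1/12 + 1/12 + 0.90²/48) = 0.43, so the 95% CI is 0.90 ± 0.84. For the difference between two such effects in one session, the SE is √2 × 0.43 = 0.61 and the half-width is about 1.19. Attrition would widen both. Only a very large difference between outcomes could be shown, and the report should say so.

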**Additional exploratory aims are:**

**Aim 4:** Optimal Neural Targets for iTBS using Group Iterative Multiple Model Estimation (GIMME) based on *ab a priori* fixed network structure comprised of 12 anatomical nodes associated with cognitive processing. GIMME will be used to identify common, subgroup and unique neural circuits of moderately cognitively impaired participants. For persons with moderate cognitive impairment resulting from TBI, we hypothesize that there will be sub-types of persons with common brain circuitry important to cognition.

**Aim 5:** Determine immediate gains in working memory and performance of complex IADL after provision of a single session of iTBS targeting to the same location in the L DLPFC that was treated and after a single session of iTBS targeting the optimal GIMME brain target. For persons with moderate cognitive impairment resulting from TBI, we hypothesize that average gains in working memory and functional performance after a single iTBS session site will be

significantly different according to site of stimulation (L DLPFC site, GIMME site).

## 5.0 Study Procedures

### 5.1 Study Design

Recruitment of Veterans will involve a multi-step process to eliminate those who would be at highest risk for adverse events related to study procedures and to identify a cohort of Veterans who meet inclusion/exclusion criteria (Figure 1). NOTE: This is for the primary study, the optional study participation will be for individuals with primary diagnosis of TBI. Veterans with diagnosis of stroke are excluded.

#### *Screening: Identifying and Recruiting Research Candidates:*

We will identify a cohort of Veterans from the corporate data warehouse (CDW) by using the ICD codes in the national inpatient and outpatient files available with VA Informatics and Computing Infrastructure. We will identify Veterans with ischemic stroke or TBI admitted to a rehabilitation bed and/or seeking outpatient rehabilitation services (i.e. OT, SLP) from Hines VA in the previous 10 years. We will filter and sort this list to exclude primary diagnoses other than ischemic stroke or TBI, any dementia diagnoses, deaths and enrollment in extended care. We will then re-sort the list by primary and co-occurring diagnoses, gender, age, date of most recent neurologic event, comorbid medical conditions including seizure disorders, by last date of a VA rehabilitation service, and by prescribed medications (by first and last fill date as well as dose). To maximize likelihood of medical stability, Veterans with changes in medications and/or dose within 3-months of list extraction will be excluded. We will use the sorted list to minimize heterogeneity by excluding Veterans with both ischemic stroke and TBI, receiving anti-epileptic medications to control seizures or have a documented seizure three months prior to list extraction, and Veterans with these comorbid medical conditions: congestive heart failure, implanted pacemakers, defibrillators and/or cochlear implants. We anticipate having at least

1,500 Veterans remaining on the list from which we will randomly sample 500 males (250 with ischemic stroke, 250 with TBI) who will each be sent recruitment letters. We anticipate a smaller percentage of female Veterans on the list, therefore we will send a recruitment letter to all female Veterans to reduce risk of results being non-representative across biological sex. The letter will introduce the study and inform Veterans that researchers will be contacting them by telephone, text, and/or email to determine study participation interest. Veterans will be contacted up to 5 times. To determine interest in study participation, male Veterans will be contacted according to the order of the randomized list. During telephone contact, male Veterans expressing interest in study participation will continue with the telephone call to start screening. All female Veterans will be contacted and those expressing interest, will also continue with the telephone call to start screening.

***Telephone Screening-Part 1: Stabilization of Functional Recovery and Medical Status:***

Considering that the nature, severity and recovery of functional capabilities vary widely within and between ischemic stroke and TBI as well as by sex, the Veteran and/or healthcare surrogate will be asked to report current rehabilitation services (VA, non-VA) and if they experienced a seizure since their last visit to Hines VA. Veterans reporting active rehabilitation services, seizures and/or pregnancy will be excluded. Veterans who report any change in medical status since last medical evaluation will be advised to seek follow up medical evaluation. Veterans remaining eligible will complete a brief iTBS and MRI safety checklist and those without contraindications will proceed to Part-2 of the phone screening. The contraindications identified on the MRI screening form, including but not limited to ferromagnetic or other magnetic-sensitive metals implanted in their head or 30cm of the treatment coil (e.g. implanted electrodes/stimulators, aneurysm clips or coils, stents, medication pumps, intracardiac lines, bullet fragments) or implanted stimulator devised in or near the head (e.g. cardiac pacemakers, deep brain stimulators, cochlear implants, and vagus nerve stimulators), will be excluded.

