***Screening Medical Records:***

The VA electronic medical record and any non-VA medical records will be reviewed to confirm completion of rehabilitation services as indicated by inpatient/outpatient therapy reports and notes. Veterans actively receiving therapy services will be excluded. To examine medical stability, we will also confirm that medical status has remained stable for three months (e.g., new seizures, new diagnoses) prior to the records review as well as absence of other exclusionary conditions (e.g., having both TBI and ischemic stroke). We will also review medications to identify Veterans actively receiving pharmacological neurostimulants. These cases will be reviewed by the study neurologist who will consult with the prescribing physician to determine safe withdrawal, via titration. If there is question about safety, then the Veteran will be

excluded. Dictated radiology reports will be reviewed to identify Veterans with ischemic strokes bilaterally who will be excluded.

**Medication Review:** For participant inclusion and safety, if the participant is prescribed medication known to act on the CNS, an evaluation of cumulative seizure risk and appropriate risk mitigation for each patient according to their prescribed medication profile and relative to self-reported medications, alcohol consumption (AUDIT-C) and substance use (DAST-10) will be evaluated prior to enrollment. In lieu of excluding participants based on the name of any particular drugs or drug classes or limit them to a set, we will follow the procedure as described:

- Clinical experts (e.g., Research Neuropsychiatrist [name], Neuropsychologist [name], Neurologist and Epileptologist [name], Neurologist and Stroke Expert [name]) and/or scientific subject matter experts (e.g., TBI expert [name], AUD and SUD expert [name]) will review all CNS acting medications for each research candidate/participant.
- CNS acting medications will be reviewed for likelihood of seizure risk according to purpose for which the medication was prescribed, dose, speed of dose change (increase or decrease), combination with other CNS active drugs or other factors potentially contributing to lower the seizure threshold (i.e., sleep deprivation, alcohol consumption, marijuana therapeutic and recreational use).
- The determination (by clinical and/or scientific subject matter experts) of likely or plausible seizure risk will be used to make these decisions:

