### Study-Day 0 (In Person Eligibility Screening) (2-3 hours)

1. Complete questionnaires and testing
  - a. Audit-C and DAST-10

- b. Testing questionnaires
- c. Demographic information collection

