**Study-Day 1 (~5 hours) (may occur over 2 days):**

- 1. Complete tests/questionnaires that are not repeated. Some are collected for use as covariates (Table 2) and some are needed for treatment preparation.
  - a. Baseline testing battery
  - b. APT Baseline
  - c. fMRI-to be completed at NU CTI
  - d. Motor Threshold
  - e. Baseline EEG\*
- 2. Rating suitability of the number and types of tests 1-3.

\*EEG to be completed prior and reviewed by physician prior to Motor Threshold

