**Study-Day 2 (4 days after Study Day 1)(~8 hours):**

- 1. PE testing battery
- 2. A single session of **Active** iTBS or **Placebo** iTBS
- 3. Randomly assigned ImE test (MDS or AMPS), administered 3-times at 30 min intervals, each interval includes 5 to 15 min of rest).
- 4. PE testing battery
- 5. Suitability ratings 1-3

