## 5.4 Inclusion/Exclusion Criteria

**Table 1. Inclusion/Exclusion Criteria**

Inclusion Criteria	Exclusion Criteria

• Diagnosis of TBI or Ischemic Stroke

• 2-10 years post neurologic event having completed rehabilitation

• Age 18 - 80 years old

• Medically stable

• Fluent in English

• Moderately impaired cognitive function as defined by AMPS Processing sub-scale measures falling below 1.0 logits

• Moderately impaired cognitive capacity as

	

• Have BOTH TBI and Ischemic Stroke

• Intracranial lesions or hemorrhagic stroke

• Other primary neurologic diagnosis

• Any dementia diagnosis

• History of/or symptoms of psychotic spectrum disorders (i.e., bipolar, schizophrenia)

• Persons with alcohol use disorder (AUD) and/or substance use disorder (SUD) diagnoses confirmed by clinical and/or scientific experts

• Reside in an extended care facility

• Less than 2 years post TBI or ischemic stroke

• Anti-epileptic medications for seizure activity

defined by having two or more scores falling $\geq 1$ standard deviation below age normed expectations on: the RBANS index scores, DKEFS Color-Word Trials 3 and 4 scale scores, and/or WAIS-IV Digit Span scaled score	
 
Seizure within the past 3 months or active seizure
 
Contraindications to MRI/iTBS such as ferromagnetic or other magnetic sensitive metals implanted in their head or with in 30cm of the treatment coil or implanted devices in or near the head
 
Medication changes within 3 months of starting participation
 
Currently receiving therapy services
 
Pregnancy
 
FIM scores for problem solving <3 or >4 OR memory <4 or >5, or changes in FIM scores during screening process
 
Neurostimulants that cannot be safely withdrawn
 
Bilateral ischemic stroke
 
Mild or severe impairments in cognitive capacity or cognitive function
 
CHF, implanted pacemakers or defibrillators, or cochlear implants
 
Heart valve with metallic materials
 
Questionable test validity as indicated by DOT (E-score <math>\geq 17</math>) or BRIEF (Negativity <math>\geq 6</math>; Infrequency <math>\geq 3</math>; Inconsistency <math>\geq 8</math>)
 
RBANS Total Scale < 70
 

---	---

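### For Veterans seen at Hines within the past 3 months, the telephone seizure question looks back less than the 3 months that Table 1 excludes

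*Combined protocol and SAP*

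**What the plan says.** Section 5.1, Telephone Screening-Part 1, has the Veteran or surrogate report "if they experienced a seizure since their last visit to Hines VA". A reported seizure leads to exclusion. Section 5.4, Table 1, excludes "Seizure within the past 3 months or active seizure" and also "Anti-epileptic medications for seizure activity".

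Other steps bear on the same criterion:

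- **List extraction (5.1, 5.2):** removes Veterans with a documented seizure in the 3 months before extraction.
- **Telephone Screening-Part 2:** asks where non-VA emergency, intensive or post-acute care was given, so that those records can be obtained.
- **Screening Medical Records:** staff must "confirm that medical status has remained stable for three months (e.g., new seizures, new diagnoses) prior to the records review", using VA and any non-VA records.
- **Study-Day 1:** an asterisked note requires "EEG to be completed prior and reviewed by physician prior to Motor Threshold". Section 5.5 says that epileptologists read the EEG for epileptiform discharges.
- **Protection Against Risk:** seizure is one of the safety indicators followed on every study day, scored as change from baseline.

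**The concern.** The telephone call is the only point in the described screening steps where someone is asked about seizure history, as opposed to having charts searched. Self-report is what can reveal a seizure that never reached a clinician. For a Veteran recently seen at Hines, the question asks about less time than the trial's own exclusion covers. A truthful answer of no is then compatible with a seizure inside the excluded window.

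What is at stake is participant safety, not the analysis. Potential Risks names seizure induction as the main worry with TMS. Protection Against Risk acknowledges that the risk in people with brain injury or ischemic stroke is not established. All participants, in either arm, receive single TMS pulses at motor threshold testing.

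**Working it through.** No sample size, power or error rate enters this point. The check compares look-back windows.

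**Inputs.** Table 1 window: 3 months. Telephone window: t months, the time from the last Hines visit to the call. The documents give no values for t, so those below are assumed for illustration.

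**Formula.** Part of the Table 1 window that the call does not ask about = max(0, 3 − t) months.

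| Last Hines visit before the call | Calculation | Not asked about |
|---|---|---|
| a few days | 3 − (near 0) | just under 3 months |
| 1 month | 3 − 1 | 2 months |
| 2 months | 3 − 2 | 1 month |
| 3 months or more | max(0, 3 − t) | 0 |

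Beyond 3 months the telephone question is stricter than Table 1: it covers more than the excluded window, and any seizure reported still excludes.

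**What the other steps recover.** The unasked part lies before the last Hines visit.

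1. The list filter and the records review each look back a full 3 months from their own dates, but both depend on documentation. A recorded seizure in the unasked part should be found.
2. A seizure that led to treatment would probably also be caught by the anti-epileptic or medication-change exclusions.
3. The EEG looks for current epileptiform discharges; it does not take a history.

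What remains is a seizure within the past 3 months, before the last Hines visit, absent from every reviewed record and followed by no relevant drug change.

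**Who is likely to have small t.** Section 5.2 adds clinician flyers and record screening in clinics such as Neurology. Veterans reached that way may well have been seen recently. This is an inference, as no visit dates are given.

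**From screening to the first pulse.** Study-Day 2 is set 4 days after Study-Day 1, and Study-Days 3 and 4 each follow at 2 weeks. No interval is given from records review to Study-Day 0 or Study-Day 1. The study-day seizure item applies on Study-Day 1, when motor threshold is scheduled, but the readable text does not place it before the pulses or state what period it covers.

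**After rewording.** With a look-back equal to the longer of 3 months and t, the unasked part is 0 for every t.

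**The case against.** The strongest reply is that the call is one layer and enrols nobody. Section 5.5 schedules in-person screening only if all criteria are still met after both the call and the records review, so the Table 1 row binds however the telephone question is phrased. The records review names new seizures and covers the same 3 months. The telephone question can be read as its complement, picking up time since the last Hines contact. This stands, and it is why the residual is narrow. It does not remove the mismatch, because records cannot supply what was never recorded.

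A reader might go further and infer that no safeguard takes a 3-month seizure history before the first pulse. The documents do not support that: the records review takes one, from records, and precedes motor threshold.

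A reader might also infer that all 48 participants are exposed to an unchecked gap between screening and stimulation. That is not supported either. Seizure is followed on every study day, which includes Study-Day 1, and a physician reviews the EEG before motor threshold. Counting everyone who receives pulses is not counting those who could be missed. Figure 1, which summarises exclusions by screening step, and the items on the iTBS and MRI safety checklist are not visible here and may already contain a timed seizure question.

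Finally, the Table 1 seizure row gives no reference date, while the medication row reads "Medication changes within 3 months of starting participation". That is a difference in drafting. A 3-month window in an eligibility table reads naturally as counted back from the eligibility decision, so it is not a separate defect.

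**Conclusion.** The point holds in a limited form, as a minor safety-consistency matter to consider. For Veterans seen at Hines within the past 3 months, the telephone question falls short of Table 1 by 3 months minus the time since that visit, which is just under 3 months at most. Only an unrecorded seizure in that stretch could be missed. The number of such Veterans cannot be estimated from the documents and is probably small.

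The timing of the study-day seizure item on Study-Day 1 is a clarification rather than a demonstrated gap. It falls away if Figure 1 or the checklist already settles it; the telephone wording quoted above would still differ from Table 1. Neither matter affects sample size or analysis.

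**What to change.** **Main change.** Reword the question in Telephone Screening-Part 1 to ask about any seizure in the past 3 months or since the last Hines visit, whichever is longer. Keep the exclusion of anyone who reports one. The longer-of rule closes the shortfall without relaxing the present question for Veterans last seen more than 3 months ago.

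**Secondary clarification.** Unless Figure 1 or the iTBS and MRI checklist already provides for it, state that the seizure item followed on each study day is asked on Study-Day 1 before the motor threshold pulses, alongside the EEG review, and covers the time since screening.

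The list-extraction filter, the records-review window and Table 1 can stay as they are. The cost is one reworded question and one sentence on the order and coverage of an item already collected, with no new visit, procedure or staff.
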